5. High Risk with Explanation Based on Algorithm - Patients in this treatment arm received messages telling them they were identified to be at high risk for flu complications via analysis of their medical records by a computer algorithm.

Power Analysis

The sample size above allows 80% power to detect an increase in flu vaccination rates from 35% to 37.1% with two-tailed alpha = .05 for any comparison between study arms.

Message Modalities

Patients randomized to arms 2-5 were sent messages in up to 3 modalities, depending on eligibility: 1. a letter, 2. a MyGeisinger (MyChart patient portal) message, and 3. a short message service (SMS) message.

Project Status

All intervention messages have been sent.

Letters for the Active Control and High Risk with Explanation Based on Algorithm study arms were sent on 9/13/22. Due to a miscommunication with the mail room, letters for the High Risk Only and High Risk Based on Medical Records arms were delayed by one day (send date of 9/14/22).

Patient portal messages were sent on 9/27/22 for all study arms.

Patients eligible for SMS were randomized to be sent a message on 10/12/22 or 10/13/22. Randomization was stratified by study arm.

Data collection is ongoing within the health system, and the study team has not yet obtained or analyzed any outcome data from the study.

Change in Primary Outcome Time Frame

Our originally preregistered primary outcome time frame was within 2 weeks of the final message send date. However, due to the mistimed letters mentioned in the Project Status section, we changed the primary outcome time frame to within 6 weeks of the patient's study start date, so all patients can be monitored for the same length of time.

The study start date corresponds to the letter send date for the patient's study arm:

- 9/13/22: Active Control and High Risk with Explanation Based on Algorithm
- 9/14/22: High Risk Only and High Risk Based on Medical Records

Because patients in the Passive Control study arm were not sent a letter, they will be randomized to a study start date of 9/13/22 or 9/14/22.

Analysis Exclusion Criteria

Patients vaccinated before to their study start date. We will remove patients from analysis who received a flu shot prior to their study start date (9/13/22 or 9/14/22, depending on their study arm), because they could not have been influenced by our nudge messages to get a flu shot.

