Additional Exploratory Analyses

1. Age and gender

While older patients tend to be aware of their increased vulnerability, younger patients may be more surprised to learn of their high-risk status. Additionally, our previous work suggests that males and females are differently likely to get vaccinated as a function of age, with younger females *more* likely to get vaccinated than males, and older females *less* likely to get vaccinated than older males.

To test the relation between flu shots, age and gender, we will run an OLS regression including binned age (18–24, 35–44, 45–54, 65+), gender, and their interaction.

Finally, we will test for an interaction between age, gender, and study arm, as people of different ages and genders may be differentially receptive to different message versions.

2. Timing of shot

We will examine outcomes over time and run regression models to test whether intervention messages influenced the timing (time elapsed since the beginning of the intervention, September 13, 2022) of flu shots.

3. Risk level

We will explore heterogeneity in flu vaccination rates within the top 11–20% of risk, and test whether effects of study arm vary as a function of risk level.

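### The exploratory timing analysis counts every patient from September 13, but arms 3 and 4 enter on September 14, which can make those arms look later by up to about a day with no message effect

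*Combined protocol and SAP*

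**What the plan says.** Under Additional Exploratory Analyses, item 2 (Timing of shot), regression models will test whether messages changed the timing of shots, measured as "time elapsed since the beginning of the intervention, September 13, 2022". That is one fixed date for every arm.

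The rest of the plan uses a patient-level date:

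- Project Status: "Letters for the Active Control and High Risk with Explanation Based on Algorithm study arms were sent on 9/13/22". The other two risk arms were mailed a day late after a mail-room error.
- Change in Primary Outcome Time Frame: "The study start date corresponds to the letter send date for the patient's study arm", with the entry "9/14/22: High Risk Only and High Risk Based on Medical Records". Passive Control patients got no letter, so "they will be randomized to a study start date of 9/13/22 or 9/14/22".
- Analysis Exclusion Criteria: "We will remove patients from analysis who received a flu shot prior to their study start date".

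The primary outcome and all six other pre-specified outcomes run from the patient's own start date. Portal messages went out on 9/27/22 in all message arms, and SMS dates (10/12 or 10/13) were randomized within arm.

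For timing, the plan does not state the model family, the contrast, the end date or how unvaccinated patients are handled. The allocation ratio is not stated either.

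**The concern.** A shot on September 13 counts as day 0 in arms 2 and 5, but removes the patient from arms 3 and 4. The earliest value that arms 3 and 4 can take is day 1. If follow-up is each patient's own 6 weeks, their last possible value is also a day later. Study arm is therefore tied to the range of values the endpoint can take.

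The analysis asks whether messages changed timing. A one-day mailing slip could be reported as risk messages slowing vaccination, or as the unexplained and medical-records messages being slower than the algorithm message.

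**Working it through.** **1. The plan's own figure.** The documents give no figure for timing. Their only computed figure is 80% power for 35% v 37.1%. With equal arms, n = 40,671/5 = 8,134.2. Then 0.021/√[(0.35×0.65 + 0.371×0.629)/8,134.2] − 1.96 = 2.79 − 1.96 = 0.83, so power is 79.7%. This reproduces the figure and fits equal allocation, which is assumed below.

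**2. Start-date offsets from September 13.** Arms 2 and 5: 0. Arms 3 and 4: 1 day. Arm 1: 0.5 day if split 1:1 (assumed).

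- Arms 3-5 v arm 2: (1+1+0)/3 − 0 = +0.67 day
- Arms 3-5 v arm 1: 0.67 − 0.50 = +0.17 day
- Arm 2 v arm 1: −0.50 day
- Arm 3 or 4 v arm 5: +1 day
- Arm 5 v arm 2, and arm 3 v arm 4: 0

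If all arms share one calendar pattern of uptake, these are about the most that the artefact can reach.

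**3. Same calendar behaviour in every arm.** The bias then comes only from the entry rule and the end date. For flat uptake with own 6-week windows, arm 2 covers days 0-41 (mean 20.5) and arms 3 and 4 cover days 1-42 (mean 21.5). The pooled shift is 2/3 × 1 = 0.667. With a common last day of 41, arms 3 and 4 have mean 21.0. They supply 82 of every 124 shots in pooled arms 3-5, so the shift is 82/124 × 0.5 = 0.331.

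The same calculation for other shapes (days, arms 3-5 minus arm 2) gives:

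| Shape of shot dates | Own 6-week window | Common end, day 41 | Own window, own-start clock |
|---|---|---|---|
| Flat | +0.667 | +0.331 | 0.000 |
| Exponential, mean 20 | +0.655 | +0.525 | 0.000 |
| Rising linearly | +0.592 | +0.161 | −0.081 |
| Peak at day 30 | +0.465 | +0.156 | −0.205 |
| Peak at day 21 | +0.333 | +0.166 | −0.333 |

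With a common end on April 30 the range over these shapes and a slower exponential is +0.13 to +0.66. Against arm 1, the shift over all shapes and end dates is +0.03 to +0.17.

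**4. Chance of a false positive.** Assume a linear model among vaccinated patients, 35% vaccinated. Arm 2 then has 0.35 × 8,134.2 = 2,847 shots and arms 3-5 have 8,541. Flat uptake over 42 days has SD √[(42² − 1)/12] = 12.1 days. With SD 12, SE = 12 × √(1/2,847 + 1/8,541) = 0.26 day.

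- A shift of 0.67 gives z = 2.57 and is declared significant about 73% of the time (54% at SD 15, 12% at SD 40).
- A shift of 0.17 gives z = 0.64 and about 10%.

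**5. Null simulations** (8,134 per arm, 35% vaccinated, exclusions as written, OLS among vaccinated patients, arms 3-5 v arm 2):

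- Own 6-week windows with flat, rising or falling daily hazard: +0.59 to +0.68 day, 65% to 80% false positives.
- Own windows with a mid-window peak: +0.15 day, 13%. Other peaked shapes gave +0.24 day (19%) and +0.30 day (27%).
- Common end date: +0.08 to +0.51 day.
- Season-long follow-up: about +0.35 day, 10%. Log-rank or Cox: about 6%.

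**6. Candidate fixes under the same null.** Own-start clock with own windows: 4% to 6% false positives for flat, rising and falling hazards, but −0.52 day and 75% for the mid-window peak. One calendar origin with common entry and end dates: about 4% to 7% for every shape. The second result follows by construction, because all arms are then observed over the same calendar days.

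**The case against.** The plan says only that regression models will be run. It does not commit to OLS on days, to pooling arms 3-5, or to a 6-week limit. The highest false-positive rates belong to one branch of an open specification; a survival analysis is hardly affected. That objection stands, and it is why the size is given as a range. A reader might infer that risk messages will appear to delay shots by two-thirds of a day whenever nothing differs. The documents do not support that. The figure needs the contrast with arm 2, equal allocation, own 6-week windows and uptake without a peak inside the window. Messages sent on 9/27 and 10/12-13 make a peak plausible.

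A single calendar origin is also defensible in itself, since season, portal and SMS dates run on the calendar. This stands too: the fault lies in combining a common origin with unequal entry and end dates. A reader might therefore infer that moving the clock to each patient's start date cures the problem. It does so if timing follows the letter date, or if uptake is flat or exponential within own 6-week windows. Otherwise it can reverse the bias, so that risk messages look falsely early.

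None of this removes the defect. Under the written rules arms 3 and 4 have no day 0, and in every shape examined the bias makes them look later.

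**Conclusion.** The inconsistency is in the text and biases a linear timing comparison in a known direction. For pooled arms 3-5 against Active Control the artefact is roughly +0.1 to +0.7 day, with false-positive rates from about 7% to about 80%. This rests on equal allocation, 35% vaccinated, analysis among vaccinated patients, and the shapes and windows examined. Arms 3 and 4 against arm 5 can differ by up to about 1 day. Against Passive Control the pooled artefact is at most about +0.17 day with a 1:1 split of its start dates. Arm 5 against arm 2 is clean.

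Severity is minor. A reader might infer that the trial's main result is compromised; it is not. The confirmatory analyses use vaccination within 6 weeks of the patient's own start date, and the timing analysis is labelled exploratory.

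**What to change.** For the timing analysis, keep one calendar origin, exclude patients vaccinated before September 14 in every arm, and end follow-up on the same named calendar date in every arm. State the model, the contrasts and the handling of unvaccinated patients. Report arm-specific contrasts, including arm 5 v arm 2 and arm 3 v arm 4, whose letters went out on the same day.

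Add a clock from each patient's own study start date as a sensitivity analysis, not as the only change. It is useful because letters to arms 3 and 4 really did leave a day later: if patients respond to the letter, a calendar clock shows that delay as a difference between arms that has nothing to do with message content.

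The cost is a sentence or two in the SAP and the loss of one day of shots in arms 2 and 5 and in the part of arm 1 assigned to September 13. No new data are needed. Project Status says that the study team has not yet obtained outcome data, so the change can be made without knowledge of results.
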